  - i) Participants with advanced stage cutaneous melanoma who have received standard therapies with proven survival benefit including prior immunotherapy with an anti-PD-1 or anti-PD-L1 containing regimen and must have progressive or recurrent disease after prior PD-1/PD-L1 directed therapy. Participants must not have received prior anti-CTLA-4 therapy in the advanced or metastatic setting. Additionally, participants with cutaneous melanoma must have also been offered mutation-directed therapy, if indicated, that has proven survival benefit; if a participant refuses such therapy, it must be documented in the medical record. No more than 1 intervening therapy is allowed but not required between prior anti-PD-1/anti-PD-L1 containing

regimen and BMS-986218. No more than 70% of the randomized participants should have had progression of disease within a period of 6 months of start of therapy with anti-PD-1/PD-L1 agent. Only cutaneous melanoma is allowed. Mucosal and uveal/ocular melanomas are not allowed; melanoma with unknown primary site may be enrolled if the investigator determines mucosal and uveal/ocular primary sites are unlikely.

j) The BMS-986218 Cohort Expansion - Monotherapy (Part 2B):

- i) Participants must have received, and then progressed, relapsed, or been intolerant to at least 2 standard systemic therapies with proven survival benefit according to their tumor types in the advanced or metastatic setting, if available. If the participant refuses or is not eligible for these regimens, the reason must be documented in the medical record. Additionally, participants must have progressed or have recurrent disease after prior immunotherapy with anti-PD-1/anti-PD-L1 either by itself or in combination with other systemic therapy agents. No more than 1 intervening therapy is allowed but not required between prior anti-PD-1/anti-PD-L1 containing regimen and BMS-986218. Participants who have been intolerant to prior immunotherapy are excluded. Prior anti-CTLA4 therapy is allowed for no more than 20% of participants, and details of treatment (including dates, doses, and response) must be available.
  - (1) Lung/NSCLC (adenocarcinoma or squamous cell carcinoma); additionally, for NSCLC, all participants with adenocarcinoma must have known EGFR, ALK, and ROS-1 status. Participants with an activating EGFR mutation, ALK translocation, or ROS-1 mutation must have received appropriate inhibitor therapy.

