### 7.4 Method of Treatment Assignment

During the screening visit, the investigative site will call into the enrollment option of the IRT designated by BMS for assignment of a 5-digit participant number that will be unique across all sites. Enrolled participants, including those not dosed, will be assigned sequential participant numbers [REDACTED]. The patient identification number

(PID) will ultimately be comprised of the site number and participant number. For example, the first participant screened (ie, enrolled) at site number 1, will have a PID of [REDACTED]. Once it is determined that the participant meets the eligibility criteria following the screening visit, the investigative site will call the IRT to centrally assign the participant into the open dose panel. If Part 1 is open upon the decision to initiate Part 2, treatment in the 2 parts will occur in parallel.

In the Randomized BMS-986218 Monotherapy Cohort Expansion in Cutaneous Melanoma (Part 2A), all participants will be centrally randomized evenly across study arms, which will include: BMS-986218 monotherapy at 7 mg, 20 mg, 70 mg Q4W or ipilimumab 3 mg/kg Q3W (maximum of 4 doses).

In the Randomized BMS-986218 Monotherapy Cohort Expansion (Part 2B), participants will be randomized evenly across study arms, which will include: BMS-986218 at 7 mg, 20 mg, and 70 mg Q4W.

In Part 2A and Part 2B, if it is decided based on a preliminary assessment of anti-tumor activity that not all arms would need to continue enrollment, randomization would continue only in the arm(s) that remain open. In addition, more subjects may be enrolled in selected arm(s) as specified in [Section 5.2](#) to better assess an initial signal.

In Part 2C Combination Expansion, multiple doses may be open concurrently. In that case, treatment assignments will alternate between the dose levels, with consecutively treated participants assigned to different parts through IRT whenever possible. If there are no openings available in the dose level to which the participant would be assigned by this algorithm, then the subject will be assigned to the next open dose.

In Part 2D Combination Expansion, participants will be assigned to one dose.

In Part 2, BMS-986218 Q4W will be administered for a maximum duration of 2 calendar years, and ipilimumab Q3W will be administered for a maximum of 4 doses.

For Part 2, participant replacement will not be allowed for participants who are discontinued after dosing.

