#### **10.1.3    *The Randomized BMS-986218 Monotherapy Cohort Expansion in Cutaneous Melanoma (Part 2A)***

The primary purpose of the Randomized BMS-986218 Monotherapy Cohort Expansion in Cutaneous Melanoma (Part 2A) is to evaluate preliminary efficacy of BMS-986218 relative to ipilimumab 3 mg/kg. One hundred and thirty two response-evaluable participants will be randomized to BMS-986218 or ipilimumab evenly across study arms (eg, 33 participants to BMS-986218 at 7 mg Q4W; 33 participants to BMS-986218 at 20 mg Q4W; 33 participants to BMS-986218 at 70 mg Q4W; and 33 participants to ipilimumab) and stratified by the outcome (ie, progressed, relapsed) of previous anti-PD-1/PD-L1 immunotherapy. Additional response-evaluable participants may be randomized to further evaluate emerging data or subgroups of interest if needed but not to exceed 40 response-evaluable participants per arm. If additional participants are randomized, up to 160 response-evaluable participants (= 40 participants  $\times$  4 arms) may be randomized in Part 2A. The ORR of ipilimumab will serve as a control. With 33 treated participants in each BMS-986218 arm, the lower limit of the 1-sided 80% confidence interval for ORR difference from ipilimumab arm will be 12%, 7.3%, or 2.7%, assuming effect size of 20%, 15%, or 10%, respectively.

Although the above assumptions on the response rate were used for the purpose of sample size calculation, it should be noted that, to date, there are no anti-tumor response data available in this post anti-PD-1/PD-L1 population. The efficacy evaluation criteria may evolve by the time when the tumor data from this study are matured for evaluation.

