**Table 10.3.1-1: Efficacy - Statistical Analyses**

Endpoint	Statistical Analysis Methods
ORR is defined as the proportion of all treated participants whose BOR is either CR or PR by Investigator per RECIST v1.1 or per PCWG 3 criteria for prostate.  BOR for a participant will be assessed per RECIST v1.1 by Investigator, unless otherwise specified.	Estimate of ORR and corresponding 2-sided exact 95% CI using the Clopper-Pearson method by treatment for each tumor type.  For part 2A, estimate of difference in ORR between arms (using ipilimumab as reference) and corresponding 2-sided exact 95% CI using the Clopper-Pearson method by BMS treatment arms.
Median DOR  DOR for a participant with a BOR of CR or PR is defined as the time between the date of first response and the date of the first objectively documented tumor progression per RECIST v1.1 or per PCWG 3 criteria for prostate, or death, whichever occurs first.	Estimate by the Kaplan-Meier method and corresponding 2-sided 95% CI using Brookmeyer and Crowley methodology (using log-log transformation) by treatment for each tumor type.
PFSR at 24, 36, and 48 weeks  PFS for a participant is defined as the time from the first dosing date to the date of first objectively documented disease progression or death due to any cause, whichever occurs first.	Estimate PFSR by the Kaplan-Meier method and corresponding 2-sided 95% CI using Greenwood formula by treatment for each tumor type.  For part 2A, estimate difference in PFSR between arms (using ipilimumab as reference) by the Kaplan-Meier method and corresponding 2-sided 95% CI using Greenwood formula by BMS treatment arms.  Estimate median PFS by the Kaplan-Meier method and corresponding 2-sided 95% CI using Greenwood formula by treatment for each tumor type.

Abbreviations: BOR = best overall response; BMS = Bristol Myers Squibb; CI = confidence interval; CR = complete response; DOR = duration of response; ORR = objective response rate; PCWG 3 = Prostate Cancer Working Group; PFSR = progression-free survival rate; PR = partial response; RECIST = Response Evaluation Criteria in Solid Tumors.

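### Part 2A's ORR and PFSR differences from ipilimumab use neither the randomisation stratification factor nor the capped early-progression factor

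*Combined protocol and SAP*

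**What the plan says.** Section 6.1, inclusion criterion 2) i), sets a limit for Part 2A: "No more than 70% of the randomized participants should have had progression of disease within a period of 6 months" of starting an anti-PD-1/PD-L1 agent. It applies to the cohort as a whole, not to each arm, and the section does not say why it is there.

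Section 10.1.3 says randomisation to the four arms is "stratified by the outcome (ie, progressed, relapsed) of previous anti-PD-1/PD-L1 immunotherapy". The two outcomes are not defined by time to progression. Section 7.4 says that "all participants will be centrally randomized evenly across study arms" and does not mention stratification.

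Table 10.3.1-1 defines the Part 2A response comparison as an "estimate of difference in ORR between arms (using ipilimumab as reference") with a two-sided 95% interval. The PFSR comparison is a Kaplan-Meier difference with Greenwood variance. Neither entry names a stratum or covariate. Section 10.3 presents these entries as a summary, with the SAP to be finalised before database lock.

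**The concern.** A factor used to stratify randomisation would normally appear in the analysis. If it does not, the balance achieved by design is not reflected in the standard error. Here the analysis table leaves out the trial's own stratification factor.

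Early progression on prior therapy is a second factor. Someone has to track it to enforce the limit, but the limit controls only the overall mix. Two arms of 33 can still differ noticeably in their share of early progressors. If response differs between early and later progressors, that imbalance passes directly into the difference from ipilimumab. What is at stake is how each of the three dose-versus-ipilimumab contrasts is read, in a cohort whose planned margins are narrow.

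**Working it through.** **Inputs from the documents.** 33 participants per arm and four arms, 132 in total (Section 10.1.3: "With 33 treated participants in each BMS-986218 arm"); even allocation (Section 7.4); an early-progressor share of at most 70% (Section 6.1); effect sizes of 20, 15 and 10 points (Section 10.1.3).

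**Assumptions.** Control ORR is not stated. The gap in ORR between later and early progressors is taken as 5 to 20 points, the same in both arms. Section 10.1.3 says "there are no anti-tumor response data available in this post anti-PD-1/PD-L1 population", so neither can be sourced.

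**1. The plan's own figure.** Section 10.1.3 states that "the lower limit of the 1-sided 80% confidence interval for ORR difference from ipilimumab arm will be 12%, 7.3%, or 2.7" per cent, "assuming effect size of 20%, 15%, or 10%, respectively". Use the unpooled limit d − 0.8416 × √{[pc(1−pc) + pt(1−pt)]/33}, with pt = pc + d and pc = 10%:

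- d = 20%: SE = √(0.3000/33) = 0.0953; limit 11.98%
- d = 15%: SE = √(0.2775/33) = 0.0917; limit 7.28%
- d = 10%: SE = √(0.2500/33) = 0.0870; limit 2.67%

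All three match. Control rates of 5%, 15% and 20% do not (5%, for example, gives 12.9, 8.3 and 3.9%), so the 10% is back-solved.

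**2. Chance imbalance in early progression, if nothing balances it.** The SD of the difference in shares is √[2f(1−f)/33]:

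- f = 0.7: √(0.42/33) = 11.3 points
- f = 0.6: 12.1 points
- f = 0.5: 12.3 points

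Holding the cohort total at 92 early progressors of 132 (70%), a simulation gives an SD of 11.4 points. A single comparison is out of balance by 15 points or more in 23% of trials and by 20 points or more in 8%. For at least one of the three comparisons with ipilimumab, the figures are 49% and 20%.

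**3. Shift in the ORR difference** = imbalance × gap:

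- 1 SD: 11.3 × 0.05 = 0.6 points; 11.3 × 0.20 = 2.3 points
- 20-point imbalance: 20 × 0.05 = 1 point; 20 × 0.20 = 4 points

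For scale, the 95% half-width (Wald approximation) is 1.96 × SE, or 18.7, 18.0 and 17.1 points at the three effect sizes.

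**4. Precision gained by stratifying on early progression.** Replace each p(1−p) by 0.7e(1−e) + 0.3l(1−l), where e = p − 0.3 × gap and l = p + 0.7 × gap. The largest gain is at a gap of 20 points and d = 10%:

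- control: e = 4%, l = 24%, giving 0.0816
- active arm: e = 14%, l = 34%, giving 0.1516
- SE = √(0.2332/33) = 0.0841; limit 2.93%

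This is 0.26 points above 2.67%. Over gaps of 5 to 20 points the three limits become 12.0–12.2%, 7.3–7.5% and 2.7–2.9%. On the 95% scale the half-width falls by at most 1.96 × (0.0870 − 0.0841) = 0.6 points.

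**5. PFSR.** The mechanism is the same. The documents give no PFSR assumption, so its size is not computed.

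**The case against.** The strongest reply is that nothing here is invalid. Under concurrent randomisation, chance imbalance does not bias the crude difference, and the unadjusted interval already allows for it. Section 3.2.1 says no prospective hypotheses are formally evaluated, and the SAP is still to be written. A shift of 0.6 to 2.3 points is small beside a half-width of 17 to 19. All of this stands. It limits the point to interpretation and a small gain in precision.

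The randomisation factor concerns the same prior treatment and may partly balance early progression. This also stands. The overlap is unknown because the outcomes are not tied to 6 months, so the SDs in step 2 are upper bounds at each prevalence.

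Some stronger readings are tempting but not supported:

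- **That the limit shows the sponsor regards early progression as prognostic.** Section 6.1 gives no reason. Section 5.4.2 distinguishes primary from acquired resistance, and Part 2C enrolment may favour participants with disease control beyond 6 months on prior therapy. Both make the inference plausible, but neither states it.
- **That the ORR difference could move by about 5 points.** This takes a 2-SD imbalance and a 20-point gap (2 × 12.3 × 0.20 = 4.9). With 10% ORR overall and 70% early progressors, that gap means 4% against 24% response, and no source in the documents supports it.
- **That the imbalance is systematic.** Section 7.4 lets arms close while others continue, so a binding limit could feed later progressors only into the open arms. Both events are permitted, but neither is planned.
- **That the 6-month status is a recorded data field.** Table 2-1 lists only prior cancer therapies. Recording is implied by the need to enforce the limit, but is not stated.

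**Conclusion.** The point holds as a refinement to the analysis, not as a flaw that undermines Part 2A. Table 10.3.1-1 specifies comparisons with ipilimumab that use neither the factor the trial randomises by nor the factor whose share it limits.

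The SD of imbalance in early progression is at most about 11 points at 70% prevalence. The resulting 1-SD shift in the ORR difference is about 0.6 to 2.3 points, resting on the assumed gap of 5 to 20 points. The precision gain is at most about 0.3 points on the design lower limit and also assumes a 10% control ORR. A shift near the top of that range would be close to the plan's 2.7% limit at a 10-point effect, which is the main reason to show an adjusted estimate beside the crude one.

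**What to change.** In Table 10.3.1-1 and the SAP:

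- Specify the Part 2A ORR difference with Mantel-Haenszel weights over the randomisation stratification factor. Name an interval method for the weighted difference, since Clopper-Pearson applies to a single proportion.
- Specify a correspondingly stratified Kaplan-Meier PFSR difference at 24, 36 and 48 weeks.
- Add early progression (within 6 months of starting anti-PD-1/PD-L1, yes or no) as a further stratum, or as a sensitivity analysis if cells are sparse. Confirm that the status is recorded for each participant.
- Report the unadjusted differences alongside.

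The cost is a few lines of specification and some additional output, with no change to sample size or conduct. The downside is sparse strata: two binary factors give four cells averaging 33/4, or about 8 participants per arm, and an ORR of 10 to 20% gives only about 3 to 7 responders per arm in total. The stratified PFSR estimate will feel this most at the later time points. A rule for collapsing strata should therefore be set in advance.

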### 3) Physical and Laboratory Test Findings

- a) Adequate hematologic function for participants as defined by the following:
  - i) Neutrophils  $\geq 1,500/\mu\text{L}$ .
  - ii) Platelets  $\geq 80 \times 10^3/\mu\text{L}$  (transfusion to achieve this level is not permitted within 2 weeks of first study treatment administration).
  - iii) Hemoglobin  $\geq 8 \text{ g/dL}$  (transfusion to achieve this level is not permitted within 2 weeks of first study treatment administration).
- b) Adequate hepatic function.
  - i) ALT and AST  $\leq 3 \times$  upper limit of normal (ULN).
  - ii) Total bilirubin  $\leq 1.5 \times$  ULN (except participants with Gilbert's Syndrome who must have normal direct bilirubin).
- c) Normal thyroid function or stable on hormone supplementation per Investigator assessment.
- d) Serum creatinine  $\leq 1.5 \times$  ULN or creatinine clearance (CrCl)  $\geq 40 \text{ mL/min}$  (measured using the Cockcroft-Gault formula below):

$$\text{Female CrCl} = (140 - \text{age in years}) \times \text{weight in kg} \times 0.85$$

72  $\times$  serum creatinine in mg/dL

$$\text{Male CrCl} = (140 - \text{age in years}) \times \text{weight in kg} \times 1.00$$

72  $\times$  serum creatinine in mg/dL

- e) Ability to comply with treatment, PK and pharmacodynamic sample collection, and required study follow-up periods.

f) All toxicities attributed to systemic prior anti-cancer therapy other than alopecia must have resolved to Grade 1 (National Cancer Institute [NCI] Common Terminology Criteria for Adverse Events [CTCAE] version 4.03 [v4.03]) or baseline before administration of study drug.

**4) Age and Reproductive Status**

- a) Males and females aged at least 18 years old.
- b) Women of childbearing potential (WOCBP) must have a negative serum or urine pregnancy test (minimum sensitivity 25 IU/L or equivalent units of human chorionic gonadotropin) within 24 hours prior to the start of study treatment.
- c) WOCBP must agree to follow instructions for method(s) of contraception ([Appendix 4](#)) for the duration of combination therapy treatment with study treatment BMS-986218 plus 5 months after the end of study treatment. WOCBP receiving monotherapy treatment with BMS-986218 or ipilimumab must agree to follow instructions for method(s) of contraception for the duration of monotherapy treatment with BMS-986218, or ipilimumab plus 3 months after the end of study treatment. Local laws and regulations may require use of alternative and/or additional contraception methods. See [Appendix 4](#).
- d) WOCBP who are continuously not heterosexually active are also exempt from contraceptive requirements but should still undergo pregnancy testing as described in this section.
- e) **Not applicable per Protocol Amendment 06:** Male participants who are sexually active with WOCBP must agree to follow instructions for method(s) of contraception ([Appendix 4](#)) during combination treatment with study treatment BMS-986218 and nivolumab, plus 5 half-lives of nivolumab (~ 125 days), plus 90 days (duration of sperm turnover), for a total of 215 days post-treatment completion. Males who are sexually active with WOCBP must agree to follow instructions for methods of contraception during monotherapy treatment with BMS-986218 or ipilimumab plus 5 half-lives (~ 75 days) of BMS-986218 or ipilimumab plus 90 days (duration of sperm turnover) for a total of 165 days post-treatment completion. In addition, male participants must be willing to refrain from sperm donation during this time.
- f) **Not applicable per Protocol Amendment 06:** Azoospermic males are exempt from contraceptive requirements. WOCBP who are continuously not heterosexually active are also exempt from contraceptive requirements, but still must undergo pregnancy testing as described in this section.
- g) No additional contraceptive measures are required to be used in males.

Investigators shall counsel WOCBP on the importance of pregnancy prevention and the implications of an unexpected pregnancy. Investigators shall advise on the use of highly effective methods of contraception ([Appendix 4](#)), which have a failure rate of < 1% when used consistently and correctly.

## 6.2 Exclusion Criteria

### 1) Target Disease Exclusions

- a) Participants with primary CNS malignancies, or tumors with CNS metastases as the only site of disease, will be excluded. Participants with controlled brain metastases; however, will be allowed to enroll. Controlled brain metastases are defined as no radiographic progression for at least 4 weeks following radiation and/or surgical treatment (or 4 weeks of observation if no intervention is clinically indicated), and no longer taking steroids for at least 2 weeks prior to first dose of study treatment, and with no new or progressive neurological signs and symptoms.

### 2) Prohibited Treatments

- a) Cytotoxic agents, unless at least 4 weeks have elapsed from last dose of prior anti-cancer therapy and initiation of study therapy.
- b) Non-cytotoxic agents, unless at least 4 weeks or 5 half-lives (whichever is shorter) have elapsed from the last dose of prior anti-cancer therapy and the initiation of study therapy. If 5 half-lives is shorter than 4 weeks, agreement with the Sponsor/Medical Monitor (or designee) is mandatory.
- c) Prior immunotherapy treatments, unless at least 4 weeks or 5 half-lives (whichever is shorter) have elapsed from the last dose of immune therapy and initiation of study therapy.
- d) Prior participation in an anti-CTLA-4-NF clinical study or therapy.
- e) Participants who have received prior curative radiation therapy must have been completed at least 4 weeks prior to study drug administration. Prior focal palliative radiotherapy must have been completed at least 2 weeks before study drug administration.
- f) Continued luteinizing hormone-releasing hormone (LHRH)/gonadotropin-releasing hormone (GnRH) agonist therapy in men with castration-resistant prostate cancer after progression on an initial androgen deprivation regimen is allowed.
- g) Any botanical preparation (eg, herbal supplements or traditional Chinese medicines) intended to treat the disease under study or provide supportive care within 4 weeks prior to treatment. If less than 4 weeks have elapsed from the last botanical supplement and the initiation of study treatment, the participant can be treated at the Investigator's discretion and after discussion and agreement with the Sponsor/Medical Monitor (or designee).
  - i) Use of marijuana and its derivatives for treatment of symptoms related to cancer or cancer treatment are permitted if obtained by medical prescription or if its use (even without a medical prescription) has been legalized locally.

